There are seven items in total (sleep, mood/depression, stress/anxiety/worry, energy, exercise levels, social activity and engagement in hobbies) and participants will be asked to select one of the following response options associated with each item: 'Better', 'Same' or 'Worse' (since starting the program). For participants who select 'Better' on any given item, they will be followed up with an item targeting perceived stage of the program where the change/benefit for that domain was noticed (e.g., sleep started to improve after module 3).

5. *Sociodemographic characteristics*

The following sociodemographic characteristics will be collected on enrolment (BQ, Appendix A.2) to gather descriptive information about which participants were drawn to and retained in the study:

- Diagnosis and Treatment details (type and date of diagnosis, treatments undergone)
- Age/date of birth
- Sex (Male, Female, Another term (specify))
- Country of birth, language spoken
- Education status
- Marital status
- Employment status

REFRESH: Finding New Energy after Cancer

Data Analysis

Analyses will include all available data and will be performed in R (reference index version 3.6.1 or higher). Responses to PROMs will be scored according to author guidelines. Standard recodes will be applied, as required, for analysis and reporting purposes.

Counts and percentages will be used to summarise missing data, including missing items and forms, for each measure at baseline and post-baseline assessments. Values for missing forms (i.e. PROMs) will not be imputed.

Descriptive statistics will be used to summarise patient demographic and clinical characteristics of all patients enrolled on the study. These will include counts and percentages for nominal and crude-scale ordinal (<10 levels) valued variables; and means and standard deviations or medians and interquartile ranges, as appropriate, for fine-scale (≥10 levels) ordinal and continuous valued variables.

The main feasibility outcomes are acceptability, fidelity and practicability of the stepped-care CBT intervention, including recruitment, retention, adherence and costs. Recruitment data will be summarised using a rate and 95% CI using the Poisson distribution. Adherence and retention data will be summarised using a proportion and 95% CI; this will be estimated using the Wilson method. Descriptive statistics will also be used to summarise acceptability and feasibility.

Changes from baseline at follow-up assessments for fatigue (FACIT-F), self-efficacy (PSEFSM) and Quality of Life (Ed-5D-5L) will be analysed descriptively (means and standard deviations). This will be done separately for patients who participate in Step 1 only and for those who participate in Steps 1 and 2. Effect size estimates (i.e. standardised measures of change from baseline; in this case, mean change divided by the baseline standard deviation), as described by Kazis and colleagues, will be used to characterise the size of observed differences (Kazis, Anderson, & Meenen, 1989)

Free text items from participant questionnaires will be summarised using content analysis, whereby the content of free responses will be coded and grouped, where applicable. It is worth noting that free text items mostly accompany pre-determined response options, so it is not envisaged that all participants will opt to respond to free text items.

ETHICAL CONSIDERATIONS

This project will be conducted according to the NHMRC national Statement on Ethical Conduct in Human Research (2007 and updates) and the World Medical Association of Helsinki (2013 and updates).

Informed Consent

To ensure that participants do not feel obligated to participate, the study team will ensure invitees that participation is voluntary and that they may stop their involvement in the project at any time. The study team will explain that their decision will not impact on their care or their relationships with hospital staff.

REFRESH: Finding New Energy after Cancer

Data storage and privacy issues

A unique study identification number system will be used for all data collection for this project. This system will employ the use of paired tracking numbers, so identifiable participant information (e.g., name, date of birth) and participant contact details (e.g., email and phone number) is kept separate from questionnaire responses. Therefore, participant's personal details cannot be linked with their research involvement and questionnaire responses unless you have access to the paired tracking numbers, which will be stored in an electronic password protected excel spreadsheet that is only accessible by the research team.

All questionnaire responses will be entered into a secure password protected REDCap database. Hardcopy questionnaires and PICF's will be stored in a locked filing cabinet at PMCC Department of Psychology. Only members of the research team will have access to this data, in accordance with the National Statement on ethical Conduct in Human Research 2007 and Australian Code for Responsible Conduct of Research 2018. Five years after publication or dissemination of project outcomes, hard-copy and electronic data will be destroyed.

Confidentiality

It is not expected that participating in this research project will pose any risks of harm to participants. If any disclosures of risks to safety (e.g., suicidal ideation) occur during any stages of the project, standard clinical processes will be followed including safety planning with the participant, and advising a support person of the participant (e.g., trusted family member) and where applicable a member of their treating team. This limit to confidentiality is included in the PICF.

Distressed Participants

It is not envisaged that participating in the REFRESH program will lead to participant distress. Patients that are reporting extreme distress at baseline (e.g., risk of harm, psychotic symptoms) are excluded from the study and will be referred to more appropriate acute psychological intervention. However, in the event that a participant becomes distressed throughout participation in either STEP 1 or STEP 2 of the REFRESH program, a member of the lead project team, all of whom are trained in managing distressed patients, will contact the participant and discuss support options. Participants who disclose or appear to be experiencing distress during support emails or phone calls will also be contacted to discuss support options. For example, a referral to appropriate professional support (e.g., existing hospital or community psychologist patient is already engaged with, Cancer Council Victoria telephone counselling, Employee Assistance Program). Further, participants who report feeling too distressed/unable to engage with the self-help program booklet within two weeks of commencing the program (STEP 1), will be fast tracked to individual support. Weekly contact with participants also ensures the risk of undetected distress is minimal.

REFRESH: Finding New Energy after Cancer

REFERENCES

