 - has an objective partial or complete tumour response by computed-tomography based imaging, or partial or complete metabolic response by positron emission tomography for a duration greater than 3 months
OR
 - iii. Diagnosed with a **haematological cancer** AND
 - a partial or complete response as demonstrated by routine response assessment (ie Imaging or pathology) after at least 3 months treatment with long term therapy OR
 - have previously demonstrated partial or complete response by routine response assessment post intensive treatment and have completed at least 3 months of maintenance therapy or observation OR
 - has not received treatment for a chronic blood cancer due to being below treatment threshold (e.g. indolent disease)

Participant exclusion criteria

- Insufficient English
- At clinical screening interview (see Figure 2) is identified as
 - likely experiencing a significant sleep disorder and would better benefit from our usual care CBT sleep intervention (CAN-Sleep) and/or
 - experiencing psychosis, significant psychological distress or risk of suicide or self-harm
 - not been experiencing *persistent* fatigue (i.e., symptom duration too brief-see Appendix A: clinical screening eligibility checklist)

REFRESH: Finding New Energy after Cancer

Withdrawal criteria

We do not expect that participants will be withdrawn by the research team or therapist involved in delivering the intervention. If participants require referral to other practitioners for complementary care (e.g., medication), or care for unrelated morbidity, this will be recorded on the database.

Participants who opt to withdraw from the study will be asked if they consent to continue completing follow-up measures relevant to the highest Step completed and also asked for any existing data to be included in analyses. If consent is not given to the latter, their data will be erased from the database and any records, paper or electronic, will be destroyed at the completion of the study. Participants will be unable to withdraw their data at the completion of the study as their data may have already been used.

Procedures

The study procedure is outlined in detail in Figure 2 (page 11).

Recruitment processes

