- Participants will be asked for their feedback on each Chapter of the self-management booklet as they are working through STEP 1. There are approximately 5 brief questions at the end of each chapter in the booklet. These feedback questions can be removed from the booklet and sent to the research team via email or mail by participants (see TIME 1 Questionnaire PART A (T1Q-A) in Appendix A.3).
- At the completion of the week 5 phone call, participants will be emailed a link to PART B of the TIME 1 online questionnaire (or a paper copy if preferred) (T1Q-B) (see Appendix A.4).
- The FACIT-F score from the T1Q-B will determine eligibility for STEP 2. Participants with a FACIT-F score of 10 or more points higher than baseline will finish their CBT Fatigue treatment, unless they score below 34 (severe). This was established a clinically important improvement (Reddy, Bruera, Pace, Zhang, & Reyes-Gibby, 2007).
- Participants with a FACIT-F score on the T1Q-B questionnaire of less than 10 points higher than baseline and/or below 34 will be offered STEP 2. The decision to be 'stepped up' to STEP 2 will also be made in conjunction with the psychologist's clinical judgement/interview at the week 5 phone-call of STEP 1 (e.g., if questionnaire measures don't appear congruent with clinical observations of further support needs).
- Participants who do not go on to STEP 2 of the program will complete Time 2 Part B Questionnaires (T2Q-B) (see below) 6 weeks after completing the self-management booklet, with the exception of the feasibility, acceptability and satisfaction measures (which will not be applicable as they will have not completed STEP 2).

Recruitment to STEP 2: Administration of Individual CBT

[figure not shown]
- Participants eligible for STEP 2 will be offered up to 4 CBT sessions with a clinical psychologist. These sessions can be delivered one-on-one or in a small group and via face to face or via Telehealth modalities. For Telehealth sessions a secure allied health telehealth platform called CoViu (recommended by the Australian Psychology Association) or the Peter Mac telehealth platform will be utilised.

Administration of TIME 2 Questionnaires (following STEP 2)

- After the participant's last CBT session, PART A of the TIME 2 Questionnaire (T2Q-A) will be administered (either in person or via Telehealth) (Appendix A.5).

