- b. Intervention satisfaction will be assessed by administering the Client Satisfaction Questionnaire (CSQ) (Attkisson & Zwick, 1982). The CSQ is a well validated 8-item measure of the quality of the intervention, the extent to which the program met participant's needs, perceived increases in skills, and whether participants would recommend the program to others. Total scores range from 8 to 56, with higher scores indicating greater satisfaction. The CSQ will be administered in the T1Q-B and T2Q-B assessments where applicable (appendix A.4 and A.5).
Intervention satisfaction will also be evaluated in part A of the administered questionnaires (T1Q-A and T2Q-A) with open ended items such as "Is there anything you particularly liked or disliked about Chapter 2?" or "Did you find the week 5 phone call helpful?" (see Appendix A.3 and A.5); items designed to elicit participants' own perceptions about their satisfaction with the self-management booklet and the individual CBT sessions (if applicable).
- c. Rate of recruitment to / enrolment in program will contribute to evaluation of acceptability. Numbers of referrals received, eligible and enrolled participants, withdrawals and reasons for decline/ withdrawal) will be recorded in a spreadsheet to enable calculation of rates of program uptake, dropouts and factors related to non-participation.

Cost of Intervention Delivery (Clinical Feasibility)

Intervention procedures and costs will be evaluated by documenting and measuring the different activities employed to implement the intervention (e.g., direct and indirect therapy time (includes phone support and notes) x hourly rate), time taken to complete activities x hourly rate of clinician, in addition to costs of materials and program administration time per participant (e.g. screening, scheduling) x AHA hourly rate. (Does not include study related tasks e.g. information and consent). See Table 2.

Table 2: Clinical Feasibility: Intervention Procedures and Costs

Activity	Variables	Data Collected	Cost p/Unit
Screening	
 Initial screening by existing staff Stage 2 screening via checklist implementation 	
 Role of person screening. Time taken for initial screen 	

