Appendix A Participant Questionnaires

REFRESH STUDY MEASURES SUMMARY

Measure Name	Number of items
A.1 REFRESH screening checklist (clinician use only)	Total = 18
A.2: BASELINE QUESTIONNAIRE (BQ)	Total = 39
Sociodemographic Items	15
The Functional Assessment of Chronic Illness Therapy - Fatigue (FACIT-F)	13
Perceived Self Efficacy for Fatigue Self Management (PSEFSM)	6
European Quality of Life 5 Dimension 5 Level (EQ-5D-5L)	5
A.3: TIME 1 QUESTIONNAIRE PART A (T1Q-A)	Total = 30
Booklet Chapter Feedback Questionnaire (self-devised)	6 (p/chapter)
A.4: TIME 1 QUESTIONNAIRE PART B (T1Q-B)	Total = 48
FACIT-F	13
PSEFSM	6
EQ-5D-5L	5
Acceptability of Intervention Measure (AIM)	4
Intervention Appropriateness Measure (IAM)	4
Feasibility of Intervention Measure (FIM)	4
Client Satisfaction Questionnaire (CSQ)	8
Perceived changes to personal, social and lifestyle factors (self-devised)	4
A.5: TIME 2 QUESTIONNAIRE PART A (T2Q-A)	Total = 7
Perceived satisfaction with STEP 2 (self-devised)	7
A.6: TIME 2 QUESTIONNAIRE PART B (T2Q-B)	Total = 48
FACIT-F	13
PSEFSM	6
EQ-5D-5L	5
Acceptability of Intervention Measure (AIM)*	4
Intervention Appropriateness Measure (IAM)*	4
Feasibility of Intervention Measure (FIM)*	4
Client Satisfaction Questionnaire (CSQ)*	8
Perceived changes to personal, social and lifestyle factors (self-devised)	4

*Applicable for STEP 2 participants only

A FULL COPY OF EACH QUESTIONNAIRE IS PROVIDED IN A SEPARATE ATTACHMENT: 'REFRESH_MEASURES_V3_19.10.21'.

REFRESH: Finding New Energy after Cancer

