Appendix D: Example Step 1 Email Template

Example REFRESH Step 1 Support Email template (weeks 1, 3 & 4)^

Dear __,

Hello from the REFRESH Team!

It's now been one week *[insert 3 weeks/4 weeks]* since you started your journey in the REFRESH- New Energy after Cancer study.

We hope you have found the REFRESH self-management booklet helpful so far. If you have already worked through Chapter *[insert #]*, well done! We hope you have had a chance to try the *[insert name]* activity.

Having trouble/haven't started?

If for some reason, you haven't had a chance to look at the booklet *[or chapter #]* yet, that's also OK. We understand life sometimes gets in the way.

If this is the case, we would encourage you to just focus on the parts of Chapter *[insert #]* that you think are most relevant to you. Irrespective of your progress on Chapter *[insert #]* this week, we encourage you to move on to the next chapter in the coming week.

There is no right or wrong way to use the booklet. We have designed the booklet to flow in order from Chapter 1 to Chapter 5, and this is the approach we would encourage. However, any approach that works for you is OK.

We need your feedback!

Whether or not you have completed Chapter *[insert #]*, done parts of Chapter *[insert #]*, or are yet to look at Chapter *[insert #]*, we would really love your feedback!

At the end of Chapter *[insert #]*, there are 5 short questions for you. We have added these questions to help us understand whether people used the booklet, liked the booklet and whether anything got in the way of using it.

Once again, we really appreciate your time and participation.

Questions or Concerns

If you would like further support, we will call you in *[x]* week/s and can discuss any problems or questions you have then. However, if you have any questions or concerns in the meantime, feel free to reply to this email and we will endeavour to respond as soon as possible.

Kind Regards, the REFRESH team.

^Email content will be adapted and personalised in line with participant specific progress and project timeline.

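### The withdrawal rule ties follow-up to the highest Step completed, so people who withdraw mid-Step are not asked for the acceptability, appropriateness, feasibility and satisfaction scales of the Step they left

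*Protocol*

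**What the plan says.** **Withdrawal criteria.** The rule opens "Participants who opt to withdraw from the study will be asked if they consent" to further follow-up and limits that follow-up to measures "asked if they consent to continue completing follow-up measures relevant to the highest Step completed". A separate question asks whether data already collected may be used.

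**When the scales are given.** For STEP 1, the section on TIME 1 questionnaires states: "At the completion of the week 5 phone call, participants will be emailed a link to PART B of the TIME 1 online questionnaire". For STEP 2, T2Q-A follows the last CBT session and T2Q-B follows the final one. The measures summary in Appendix A lists AIM, IAM, FIM and CSQ in T1Q-B and T2Q-B only. In T2Q-B all four are starred as "Applicable for STEP 2 participants only". The text on satisfaction agrees: "The CSQ will be administered in the T1Q-B and T2Q-B assessments where applicable".

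**STEP 1-only participants.** They receive T2Q-B six weeks after finishing the booklet, without the feasibility, acceptability and satisfaction scales.

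**Other evidence on acceptability.** Chapter feedback (T1Q-A) is gathered during STEP 1: "Participants will be asked for their feedback on each Chapter of the self-management booklet as they are working through STEP 1". Under Intervention Acceptability, item c, the numbers of withdrawals and the reasons for them are recorded.

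**Data Analysis.** Acceptability, retention and adherence are among the main feasibility outcomes. Missing questionnaires are not imputed.

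**The concern.** The rule plainly means to keep collecting data after withdrawal, but it defines what to collect by the Step a person has finished. Someone who leaves partway through a Step has, by definition, not finished it. That Step's questionnaires, which carry the scales rating it, then fall outside the request.

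People who leave partway are likely to include those whom the booklet or the sessions did not suit. The protocol wants to learn who is more or less suited to stepped-care CBT, so their ratings matter. If they are never asked, the mean AIM, IAM, FIM and CSQ scores come mainly from people who stayed. Analysis cannot repair this later, because a score that was not requested cannot be recovered and missing forms are not imputed.

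There is also a mismatch within the protocol. Data Analysis groups fatigue, self-efficacy and quality-of-life change by the Steps in which people participate, whereas the withdrawal rule goes by the Step completed. Someone who withdraws during STEP 2 is analysed with the Steps 1 and 2 group but is not asked for that group's full measures.

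**Working it through.** The point concerns wording, so the check applies the withdrawal rule to the questionnaire schedule.

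**The plan's own figures**

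- Expected STEP 2 number: 50 × 0.50 = 25, as stated. The STEP 2 part of the gap can therefore affect only about half of those enrolled.
- T2Q-B items: 13 (FACIT-F) + 6 (PSEFSM) + 5 (EQ-5D-5L) + 4 (AIM) + 4 (IAM) + 4 (FIM) + 8 (CSQ) + 4 (perceived change) = 48, as stated.
- Starred items: 4 + 4 + 4 + 8 = 20. The reduced T2Q-B therefore has 48 − 20 = 28 items.

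**The rule by point of withdrawal, read literally**

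| Withdrawal from the study | Highest Step completed | Scale scores normally in hand | Still requested | Not requested |
|---|---|---|---|---|
| During STEP 1 | None | None | Nothing | T1Q-B and T2Q-B, so no AIM, IAM, FIM or CSQ |
| During STEP 2 after fast-track | None | None (see note) | Nothing | T1Q-B, T2Q-A and T2Q-B, so no AIM, IAM, FIM or CSQ |
| During STEP 2 after completing STEP 1 | STEP 1 | STEP 1 AIM, IAM, FIM and CSQ from T1Q-B | Possibly the reduced T2Q-B (28 items) | T2Q-A and the 20 starred STEP 2 items |

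Note: the protocol does not say whether a fast-tracked participant still has the week 5 call that triggers T1Q-B. The table assumes that T1Q-B is not already in hand.

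In the last row the reduced T2Q-B is only possible, because it is assigned to people who do not go on to STEP 2. Its use for someone who started STEP 2 and then left is not spelled out.

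**Size: illustration only, all inputs assumed**

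The protocol gives no withdrawal rate. Suppose that w of 50 participants leave without any scale score, that 80% of those scored are satisfied, and that a fraction q of the leavers would have been satisfied. The proportion over all 50 is [0.8 × (50 − w) + q × w] / 50.

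| w | Among those scored | All 50, q = 0 | All 50, q = 0.5 |
|---|---|---|---|
| 5 | 36/45 = 80% | 36/50 = 72% | 38.5/50 = 77% |
| 10 | 32/40 = 80% | 32/50 = 64% | 37/50 = 74% |
| 15 | 28/35 = 80% | 28/50 = 56% | 35.5/50 = 71% |
| 20 | 24/30 = 80% | 24/50 = 48% | 34/50 = 68% |

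For w = 10, the Wilson 95% interval among those scored is 65.2% to 89.5%. That interval reflects sampling error only and says nothing about the missing leavers.

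For a mean score, the overstatement is f × d, where f is the fraction without scores and d is how much lower they would have scored. With an assumed d of 1.5 points on a 5-point item and f of 0.10, 0.20 or 0.30, it is 0.15, 0.30 or 0.45 points.

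**The case against.** The strongest reply is that the gap is narrow and that leavers are heard in other ways. Much of this stands.

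- **Withdrawing is not the same as stopping.** The rule covers withdrawal from the study. T1Q-B is triggered by the week 5 call, not by finishing the booklet, so someone who abandons the booklet but stays enrolled still receives all four scales. STEP 2 is up to four sessions, so attending fewer does not in itself remove the questionnaires. A reader might infer that the scores leave out everyone who rejected the programme. The protocol does not support that.
- **STEP 2 withdrawals are partly covered.** A reader might infer that they are due nothing new. The reduced T2Q-B may still apply, with fatigue, self-efficacy, quality of life and perceived change, and STEP 1 scale scores are normally in hand. Those scores rate the booklet, however, not the CBT sessions.
- **Other evidence covers leavers.** The support email in Appendix D asks for chapter feedback "Whether or not you have completed Chapter" or not, and withdrawal counts and reasons are recorded. These are useful, but they do not replace the standard scales.
- **Retention works the other way.** It is the proportion of enrolled participants who complete follow-up, so each withdrawal without follow-up lowers a main outcome. The results as a whole are therefore not pushed in one direction only.
- **Part of the material is not visible.** Figure 2 is not shown and the consent form was removed. Either might clarify the rule, but the rule as worded would still need to agree with it.

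Sparing people who have left a study is a legitimate choice. Here, though, the protocol has already chosen to ask them, with consent, and only the scope of the request is in question.

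**Conclusion.** The point holds in a limited form. Read literally, the rule requests no AIM, IAM, FIM or CSQ from someone who withdraws from the study during STEP 1 or after fast-track, and no STEP 2 version from someone who withdraws during STEP 2. The standard scores therefore under-represent people who withdraw, and the other evidence makes up for this only in part.

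The size cannot be derived. The illustrated figures rest on assumed withdrawal numbers and assumed scores. They also overstate what a change could recover: they treat every leaver as having no score, which is normally untrue of those who completed STEP 1, and they compare with full response, which people leaving a study will not give. They show direction and order of magnitude under the stated assumptions and do not estimate this study's bias.

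This is a stated data-collection rule and not a detail that a statistical analysis plan would settle. It merits a cheap correction and does not undermine the design.

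**What to change.** In Withdrawal criteria and the matching consent wording, change *completed* to *started*, so that the request covers measures relevant to the highest Step started. With consent, someone who withdraws during STEP 1 is then asked for T1Q-B, and someone who withdraws during STEP 2 for T2Q-A and T2Q-B, at the times these would otherwise fall due. State those times explicitly, because the present triggers are the week 5 call and the last or final session.

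Report AIM, IAM, FIM and CSQ for all responders and separately for those who completed and those who stopped early, with the number asked and the number responding in each group. It would also help to record whether each person left the programme only or the study questionnaires too.

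The cost is one changed sentence, matching consent wording and no new questionnaire. The downside is a small, voluntary extra request to people who are leaving. Only some will respond, so the gap will narrow but not close.
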